12.4.2 Statistical model, hypothesis, and method of analysis

The primary endpoint will be analyzed using a Bayesian logistic regression model. The model will include treatment group, ENA status, baseline SLEDAI-2K (< 10 , ≥ 10) as fixed effects. Weakly informative priors will be used to obtain the posterior estimates. The primary analysis will be performed for each cohort separately.

Bayesian posterior probabilities will be used to assess the following criteria as a guide for decision making ([Fisch et al 2015](#)).

Efficacy criteria (for primary endpoint):

- Week 29 responder rate in active group better than that in placebo group with high confidence (90%), i.e., $\text{Prob}(\theta_{\text{active}} - \theta_{\text{placebo}} > 0) > 90\%$, AND
- Average magnitude of effect on Week 29 responder rate $> 15\%$ over placebo, i.e., $\text{Prob}(\theta_{\text{active}} - \theta_{\text{placebo}} > 15\%) > 50\%$.

Where θ is the Week 29 responder rate, i.e. the proportion of responders per definition.

Futility criteria:

- Week 29 responder rate in active group worse than that in placebo with confidence higher than 60%, i.e., $\text{Prob}(\theta_{\text{active}} - \theta_{\text{placebo}} < 0) > 60\%$.

The posterior estimates of the treatment effect of VAY736 and CFZ533 compared to their matching placebos (along with the 90% credible intervals) at Week 29 will be provided. The results will be reported in terms of difference in probability of responders.

12.4.3 Supportive analyses

Further details of these analyses will be specified in the Statistical Analysis Plan (SAP).

12.5 Analysis of secondary endpoints

Data will be listed by treatment group, period (blinded vs. open label), subject and visit/time as appropriate. Details of statistical methodologies for secondary endpoints will be described in the SAP. Graphical presentation of the data will be performed where applicable.

12.5.1 Efficacy and/or Pharmacodynamic endpoint(s)

The PD analysis set will be used for analyses in this section.

Physician's global assessment in visual analog scale (VAS)

Physician's global assessment (PhGA) in VAS will be listed by treatment group, subject, and visit. The change from baseline in physician's VAS will be listed by treatment group, subject and visit, and summarized by treatment group and visit. Summary statistics will include mean, SD, median, minimum and maximum. A Bayesian MMRM will be applied to this endpoint, as a continuous response variable. The model will include treatment group, ENA status, baseline SLEDAI-2K (<10 , ≥ 10) and visit as fixed effects and baseline PhGA as continuous covariate. Weakly informative priors will be used to obtain the posterior estimates and unstructured covariance will be assumed.

Patient's global assessment in visual analog scale (VAS)

Patient's global assessment (PGA) in VAS will be analyzed the same way as physician's global assessment (PhGA) in VAS.

Flare

Flare determined by BILAG-2004 as below ([Isenberg et al 2005](#), [Isenberg et al 2011](#)):

- Severe flare: developing a BILAG-2004 "A" score in any system due to items that are new or worse
- Moderate flare: having two or more "B" score due to items that are new or worse

The number of flare and the rate of flare will be summarized by treatment group for different severities.

The proportion of patients with flare will be summarized by treatment group. The time to first flare will be summarized by treatment group, and listed by treatment group and subject.

12.5.2 Safety endpoints

For all safety analyses, the safety set will be used. All listings and tables will be presented by period and treatment group.

Safety summaries (tables, figures) include only data from the on-treatment period with the exception of baseline data which will also be summarized where appropriate (e.g., change from baseline summaries). In addition, a separate summary for death including on treatment and post treatment deaths will be provided. In particular, summary tables for adverse events (AEs) will summarize only on-treatment events, with a start date during the on-treatment period (*treatment-emergent* AEs).

The on-treatment period lasts from the date of first administration of study treatment until end of study (EoS).

Adverse events

All information obtained on adverse events will be displayed by treatment group and subject.

The number (and percentage) of subjects with treatment emergent adverse events (events started after the first dose of study medication or events present prior to start of double-blind treatment but increased in severity based on preferred term) will be summarized in the following ways:

1. by treatment group, primary system organ class and preferred term.
2. by treatment group, primary system organ class, preferred term and maximum severity.

Separate summaries will be provided for study medication related adverse events, death, serious adverse events, other significant adverse events leading to discontinuation and adverse events leading to dose adjustment.

The number (and proportion) of subjects with adverse events of special interest will be summarized by treatment group. A subject with multiple adverse events within a primary system organ class is only counted once towards the total of the primary system organ class.

Vital signs

All vital signs data will be listed by treatment group, subject, and visit and if ranges are available, abnormalities will be flagged. Summary statistics (e.g., change from baseline and shift tables) will be provided by treatment group and visit.

12-lead ECG

All ECG data will be listed by treatment group, subject and visit, abnormalities will be flagged. Summary statistics will be provided by treatment group and visit.

1. PR, QRS, QT, QTcF, and RR intervals will be obtained from 12-lead ECGs for each subject during the study. ECG data will be read and interpreted (/locally).
2. Categorical Analysis of QT/QTc interval data based on the number of subjects meeting or exceeding predefined limits in terms of absolute QT/QTc intervals or changes from baseline will be presented. In addition, a listing of these subjects will be produced by treatment group.

Clinical laboratory evaluations

All laboratory data will be listed by treatment group, subject, and visit and if normal ranges are available abnormalities will be flagged. Summary statistics will be provided by treatment group and visit. Shift tables using the low/normal/high/ (low and high) classification will be used to compare baseline to the worst on-treatment value.

Immunogenicity

All immunogenicity results will be listed by treatment group, subject and visit/time. Anti-VAY736 antibody and anti-CFZ533 antibody results will be listed by treatment group, subject and visit. The proportion of ADA-positive patients will be listed by treatment group and visit.

12.5.3 Pharmacokinetics

CCI

Pharmacokinetic parameters for VAY736 and CFZ533 ($C_{max,ss}$ - The highest concentration observed during a dosing interval at steady-state, and $C_{trough,ss}$ - The trough observed analyte concentration at the end of a dosing interval) will be listed by treatment group and subject. Descriptive summary statistics will include mean (arithmetic and geometric), SD, and CV (arithmetic and geometric), median, minimum and maximum.

CCI

12.5.4 PK/PD relationships

Relationships between PK and PD variables may be explored by graphical approach and descriptive statistics will be provided. Additional statistical analysis such as analysis of variance (ANOVA) or regression analysis may be performed, if necessary. Modeling of the PK and PD data may be performed as appropriate. During modeling of the PK of the study drug, the broad principles outlined in the FDA, *Guidance for Industry: Population Pharmacokinetics*, will be followed. As the PK and PD data from the current study may be pooled with data from previous study, the PK/PD analysis will be described and reported separately in a modeling plan and modelling report respectively.

12.6 Analysis of exploratory endpoints

CCI

12.6.1 Clinical Outcome Assessment

CCI

CCI

CCI

CCI

12.7 Interim analyses

CCI

12.8 Sample size calculation

12.8.1 Primary endpoint(s)

In total 120 patients are to be randomized to 4 treatment arms, aiming at 30 patients per treatment arm. The sample size may be re-estimated based on results of interim analysis 1 based on observed response rate in placebo arm.

With 30 patients in either active or the matching placebo arm, there is 84% chance that the predefined efficacy criteria ([Section 12.4.2](#)) will be met, assuming the true difference in proportion of responders is 25% in favor of active arm and placebo responder rate is 17% ([Furie et al 2017](#)). If the true difference from placebo is zero, the chance of meeting efficacy criteria is around 10%. The same assumption is made for either VAY736 or CFZ533 cohort.

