
 To evaluate the immunogenicity of multiple doses of VAY736 (s.c.) or CFZ533 (i.v.) in SLE patients 	
 Anti-VAY736 (Cohort 1) or anti-CFZ533 (Cohort 2) antibodies and incidence of ADA-positive patients

 To evaluate the pharmacodynamics (PD; rate, extent and duration of target engagement) of multiple doses of CFZ533 in SLE patients 	
 PD Cohort 2 (CFZ533): total soluble CD40 in plasma

Objective(s)	Endpoint(s)
Exploratory objective(s)	Endpoint(s) for exploratory objective(s)

Objective(s)	Endpoint(s)
CCI	

3 Study design

This is a randomized, patient- and investigator-blind, placebo-controlled, parallel-group, non-confirmatory study to assess the safety, tolerability, pharmacokinetics, immunogenicity, pharmacodynamics and preliminary clinical efficacy of multiple doses of VAY736 or of CFZ533 in patients with active SLE (see [Figure 3-1](#)).

Figure 3-1 Study design

Key study design features are as follows:

- Patient randomization into one of two treatment cohorts (VAY736 or CFZ533) and to either active or placebo
- Seven-month, placebo-controlled, blinded treatment
- Guided corticosteroid taper from Study Week 5 to Study Week 17
- A 5-month, open label treatment followed by a final outcomes assessment
- Four-month follow up for safety/PK/PD, with additional follow up for VAY736-treated patients until B cell recovery criteria are met, or up to 2 years after EoT whichever occurs earlier.

Screening and randomization

The study will randomize approximately 120 patients to test two active treatments against their matching placebo in parallel cohorts. After a 28-day screening period, eligible patients will be enrolled and stratified according to serum extractable nuclear antigens (ENA) status (positive

or negative) and baseline SLEDAI-2K score (<10 , ≥ 10). At the baseline visit, patients who are eligible for both cohorts will be randomly assigned to one of the four treatment arms. Patients who are eligible for only one cohort will be randomly assigned to either of the two treatment arms in that cohort. Randomization across the cohorts will be implemented via central randomization aiming for randomization ratio of 1:1:1:1.

Blinded treatment phase

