6.3.2 Treatment assignment, randomization

Randomization has to be performed via the IRT system at the Baseline visit at the latest. All eligible participants will be randomized to one of the available treatment arms using the IRT system. The Investigator or his/her delegate will contact the IRT system after confirming that the participant satisfies all the inclusion/exclusion criteria. The IRT system will specify a unique medication number for the package of investigational drug to the participant. The randomization number will not be communicated to the requester.

The randomization scheme for participants will be reviewed and approved by a member of the Novartis Randomization Office.

If study participants are only eligible for VAY736 Cohort (i.e., meeting exclusion criterion 1), they will be randomized to either active arm or placebo arm of Cohort 1. Otherwise, the participants will be randomized to one of four treatment arms of two cohorts.

Randomization will be stratified by ENA status (positive vs. negative) and SLEDAI-2K <10, ≥10 status at Baseline, based on screening results, in order to remove any possible confounding impact on treatment effects.

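### Protocol 12.8.1 puts the false-go rate of the two-part efficacy rule at around 10%; at the stated 17% placebo rate the joint rule gives about 6% or lower, and the 84% success figure needs restating on the same basis

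*Protocol*

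**What the plan says.** Protocol 12.8.1 sets the calculation at "With 30 patients in either active or the matching placebo arm" and assumes that "the true difference in proportion of responders is 25% in favor of active arm and placebo responder rate is 17"%, that is, 42% against 17%. On that basis "there is 84% chance that the predefined efficacy criteria" of Section 12.4.2 will be met. For no effect it says: "If the true difference from placebo is zero, the chance of meeting efficacy criteria is around 10"%. The same assumption is made for both cohorts.

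Section 12.4.2 defines the criteria as two conditions that must both hold:

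- Criterion 1: the posterior probability that the active rate exceeds the placebo rate is above 90%.
- Criterion 2, labelled "Average magnitude of effect on Week 29 responder rate" above 15% over placebo: the posterior probability that the difference exceeds 15 points is above 50%.

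The Protocol summary and SAP 7.1.3 repeat this rule. The planned analysis is a Bayesian logistic regression with treatment, ENA status and SLEDAI-2K class, run separately by cohort. The priors are described only as weakly informative. The public versions of Protocol 12.7 and SAP Section 3, on the interim analyses, are redacted.

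**The concern.** A 10% false-go rate (meeting the criteria when there is no true difference) is what a 90% posterior threshold gives when used alone. The rule in 12.4.2 adds a second condition, which at this sample size is the harder one to meet. If it has any effect, the joint false-go rate should be clearly below 10%. The stated figure looks as if the second condition changed nothing.

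The study is non-confirmatory and its criteria are a guide for decisions. The operating characteristics are therefore the main statistical justification for 30 per arm, and they tell a reader how much weight a positive result can bear. Section 12.8.1 also allows the sample size to be re-estimated after interim analysis 1 from the observed placebo rate, which presupposes a baseline calculation that can be reproduced.

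**Working it through.** **Inputs.** 30 per arm, placebo 17%, active 42%, and a zero-difference case (Protocol 12.8.1); the two thresholds (12.4.2). The documents give no prior scale. The null rate is read as 17% in both arms, the only placebo rate stated.

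**1. Attempt to reproduce 84% and 10%.** All 31 × 31 outcomes were enumerated with independent Beta priors. A go requires P(diff > 0) > 0.90 and P(diff > 0.15) > 0.50. Beta(1,1), (0.5,0.5), (1/3,1/3) and (0.17,0.83), each used in both arms, all give:

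- 17% vs 42%: **81.2%**
- 17% vs 17%: **6.0%**

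Neither stated figure is reproduced.

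**2. Why these four priors agree.** Under a vague prior, criterion 2 holds when the observed difference exceeds 15 points. Since 4/30 = 13.3% and 5/30 = 16.7%, that means at least 5 more responders on active. P(X − Y ≥ 5) is 0.812 for Bin(30, 0.42) against Bin(30, 0.17), and 0.060 when both rates are 0.17.

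A normal approximation confirms it:

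- Alternative: SE = √[(0.17×0.83 + 0.42×0.58)/30] = 0.113. Criterion 1 needs a difference of about 1.2816 × 0.113 = 0.145, below 0.15, so criterion 2 binds. P = Φ[(0.25 − 0.15)/0.113] ≈ 81.1%.
- Null: SE = √[2×0.17×0.83/30] = 0.097. Criterion 1 needs about 0.124, so criterion 2 binds again. P = 1 − Φ(0.15/0.097) ≈ 6.1%.

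**3. Criterion 1 alone.** The same four priors give 81.5 to 82.1% success and 9.6 to 10.8% false-go. At 17%, then, around 10% is the level of the first condition only.

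**4. Joint rule under other priors and models, 30 per active arm.**

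| Prior or model | Success, 17% vs 42% | False-go, 17% vs 17% |
|---|---|---|
| Beta(2,2) in both arms | 72.4% | 2.9% |
| Active Beta(1,1), placebo Beta(0.85,4.15) | 84.4% | 6.1% |
| Active Beta(0.5,0.5), placebo Beta(1.7,8.3) | 84.3% | 4.8% |
| Active Beta(1,1), placebo Beta(1.7,8.3) | 86.0% | 5.9% |
| Treatment-only logistic, N(0,10) | 81.2% | 5.9% |
| Treatment-only logistic, Cauchy 2.5 | 79.5% | 3.3% |
| Treatment-only logistic, N(0,2.5) | 77.6% | 3.0% |
| Covariates explaining 20% of variance (normal approximation) | 83.8% | 4.2% |
| Placebo arms pooled (30 vs 60) | 81.4% | 3.3% |

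Tighter normal priors lower both figures further (the tightest tried: 64.7% and 1.1%). A simulation of the logistic model with both covariates and N(0,2.5) priors (Laplace approximation, 1,200 trials per scenario) gave about 77 to 79% and 4 to 5%. Success moves with the prior; false-go at 17% stays at about 6% or lower throughout.

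**5. What would give 10%.** Under Beta(0.5,0.5), the joint false-go rate is 6.0% at a common rate of 17%, 7.2% at 20%, 8.9% at 25% and 10.2% at 30%. With active Beta(1,1) and placebo Beta(0.85,4.15) it is 10.5% at a common 25%.

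**6. At the rule's own threshold.** With 17% vs 32%, a true 15-point difference, the chance of a go is about 50% under vague priors. Section 12.8.1 does not give this.

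**The case against.** The strongest reply is that the prior is unknown to a public reader and may stand in redacted text. The four agreeing priors are all vague and the same in both arms, so their agreement does not show that the prior is irrelevant. This stands for the success figure. A placebo prior centred on 17% and worth only five patients gives 84.4% for the joint rule at 30 per arm. With a common null rate of 25%, the same prior gives 10.5%, so the stated pair can be matched if the null case used a rate other than 17%. Section 12.8.1 does not repeat the placebo rate for that case; 17% is the natural reading, but still a reading.

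Three stronger conclusions are therefore unsupported:

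- *That 84% cannot be reached.* It can, with a mild placebo-centred prior.
- *That the figures came from criterion 1 alone at 33 per arm.* That setting with Beta(1,1) does give 84.3% and 9.7%, but 12.8.1 states 30 per arm, and the origin of the figures is a guess.
- *That Cohort 2 will fall short of 30 per arm.* For patients who meet exclusion criterion 1, Section 6.3.2 does say "they will be randomized to either active arm or placebo arm of Cohort 1". But the plan is also "aiming for randomization ratio of 1:1:1:1" and allows about 10% over-recruitment, and the public text does not describe how the allocation system balances arms. No shortfall can be calculated from the documents.

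It is also fair to say that the success gap under vague priors is under 3 points, that the stated false-go rate errs on the cautious side, and that the go criteria do not depend on these planning figures. The SAP shows the study is at a late stage, with the CFZ533 results already reported. The gain now is in how the results are interpreted, not in the sample size.

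**Conclusion.** The point holds for the false-go rate. Read at 17%, the stated 10% exceeds the joint rule's value by about 4 points: about 6% under vague priors, and no more than about 6% under any prior tried at 30 per arm. Ten per cent at 17% is the level of the first condition alone. The joint rule reaches it only at a common rate of about 25 to 30%, which the text does not state.

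The success probability is a weaker point. It is about 81% under vague priors against the stated 84%, and ranges from 72% to 86% over the Beta priors tried. What was not found is 84% together with 10% at a 17% null rate.

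These results assume 30 evaluable patients per arm, each active arm compared with its own placebo arm unless noted, and, for the exact figures, conjugate Beta priors in place of the planned logistic model. The study design and decision rule are not faulted; the reported operating characteristics need correcting or explaining.

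**What to change.** In Protocol 12.8.1:

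1. Recompute both figures for the joint rule under the planned Bayesian logistic model, and state its actual prior, the assumed covariate effects and the method (simulation or enumeration).
2. Replace the 10% with the joint-rule value at a 17% common rate (about 6% under vague priors, lower under tighter ones). If another null rate was used, state it beside the figure.
3. Restate the success probability on the same basis (about 81% under vague priors). The Beta results above are a check, not the replacement figures.
4. Add the value at a true 15-point difference (about 50% under vague priors).
5. If criterion 1 values are useful, report them separately and label them as such.

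If the sponsor's calculation does yield 84% and 10%, disclosing its prior and null rate settles the point. At this stage the correction can go in the SAP or the study report. The cost is wording and one calculation; the stated power may become slightly less favourable.

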12.8.2 Secondary endpoint(s)

Not applicable.

13 Ethical considerations and administrative procedures

13.1 Regulatory and ethical compliance

This clinical study was designed and shall be implemented, executed and reported in accordance with the ICH Harmonized Tripartite Guidelines for Good Clinical Practice, with applicable local regulations (including European Directive 2001/20/EC, US CFR 21), and with the ethical principles laid down in the Declaration of Helsinki.

13.2 Responsibilities of the investigator and IRB/IEC

Before initiating a trial, the investigator/institution must obtain approval/favorable opinion from the Institutional Review Board/Independent Ethics Committee (IRB/IEC) for the trial protocol, written informed consent form, consent form updates, subject recruitment procedures (e.g., advertisements) and any other written information to be provided to subjects. Prior to study start, the investigator is required to sign a protocol signature page confirming his/her agreement to conduct the study in accordance with these documents and all of the instructions and procedures found in this protocol and to give access to all relevant data and records to Novartis monitors, auditors, Novartis Quality Assurance representatives, designated agents of Novartis, IRBs/IECs, and regulatory authorities as required. If an inspection of the clinical site is requested by a regulatory authority, the investigator must inform Novartis immediately that this request has been made.

13.3 Publication of study protocol and results

The protocol will be registered in a publicly accessible database such as clinicaltrials.gov and as required in EudraCT. In addition, after study completion (*defined as last patient last visit*) and finalization of the study report the results of this trial will be submitted for publication and posted in a publicly accessible database of clinical trial results, such as the Novartis clinical trial results website and all required Health Authority websites (e.g., Clinicaltrials.gov, EudraCT etc.).

For details on the Novartis publication policy including authorship criteria, please refer to the Novartis publication policy training materials that were provided to you at the trial investigator meetings.

13.4 Quality Control and Quality Assurance

Novartis maintains a robust Quality Management System (QMS) that includes all activities involved in quality assurance and quality control, to ensure compliance with written Standard Operating Procedures as well as applicable global/local GCP regulations and ICH Guidelines.

Audits of investigator sites, vendors, and Novartis systems are performed by auditors, independent from those involved in conducting, monitoring or performing quality control of the clinical trial. The clinical audit process uses a knowledge/risk-based approach.

Audits may be conducted to assess GCP compliance with global and local regulatory requirements, protocols and internal SOPs, and are performed according to written Novartis processes.

14 Protocol adherence

This protocol defines the study objectives, the study procedures and the data to be collected on study participants. Additional assessments required to ensure safety of subjects should be administered as deemed necessary on a case-by-case basis. Under no circumstances including incidental collection is an investigator allowed to collect additional data or conduct any additional procedures for any purpose involving any investigational drugs under the protocol, other than the purpose of the study. If despite this interdiction prohibition, data, information, observation would be incidentally collected, the investigator shall immediately disclose it to Novartis and not use it for any purpose other than the study, except for the appropriate monitoring on study participants.

Investigators ascertain they will apply due diligence to avoid protocol deviations. If an investigator feels a protocol deviation would improve the conduct of the study this must be considered a protocol amendment, and unless such an amendment is agreed upon by Novartis and approved by the IRB/IEC and health authorities, where required, it cannot be implemented.

